#### 7.6 End of study definition

The end of the study is defined as the end of the 180-day follow-up of the last patient undergoing surgery within the 85-week trial period. Data analysis shall follow this.

#### 8. STATISTICAL CONSIDERATIONS

#### 8.1 Sample size calculation

Prospectively collected data from the recently published Emergency Laparotomy Network study in 35 NHS hospitals closely match our inclusion/exclusion criteria and describe a median of 184 eligible patients aged ≥40 years per hospital per year (range 32-736) with a 30-day mortality rate of  $16.4\%^8$ . Data from the Hospital Episodes Statistics database for the year ending April 2011 gives the average 30-day mortality as 17% ( $10^{th}$  centile  $13\% - 90^{th}$  centile 22%) and the average 90-day mortality as 25% ( $10^{th}$  centile  $20\% - 90^{th}$  centile 31%). These data have been used to estimate the baseline mortality rate and between hospital coefficient of variation. Power calculations are based on the methodology proposed by Hussey & Hughes, for an analysis with fixed time effects and random cluster effects, modified to exclude data collected during the five week period in which the intervention commences in individual hospitals. The trial will be conducted in at least **90 NHS hospitals** over a period of **85 weeks** during which time we expect to receive data describing **27,540** 

**patients** undergoing emergency laparotomy. For a baseline 90-day mortality of 25%, between hospital coefficient of variation of 0.15, constant case-load (18 patients per 5 weeks per hospital) and assuming independent hospital effects, the study would achieve 92% power to detect a 12% relative risk reduction in mortality from 25% to 22% (two-sided p<0.05). This calculation is insensitive to the coefficient of variation but sensitive to the effect size. In practice, power may be reduced by correlation between hospitals within clusters and by variation in case-load between hospitals. The worst case scenario is one where each of the 15 clusters functions effectively as a single large hospital, reducing the power to 83%. This figure incorporates an adjustment for variable case-load from the pilot data. Thus the power of the study to detect a 12% relative risk reduction lies between 83% and 92%.

#### 8.2 Statistical analysis

This will be conducted on an intention-to-treat basis i.e. all patients recorded in the data base during the 85-week period will be included, and considered exposed to the intervention according to randomisation regardless of when the intervention was actually implemented. The intervention start date for each cluster will be fixed regardless of whether implementation proceeds on time. The stepped wedge design is in effect a matched design with before and after comparisons for each cluster randomised. The primary outcome will be 90-day mortality. Overall differences in 90day mortality rates between pre- and post-intervention periods will be reported. In the primary analysis, 90-day mortality will be modelled using mixed effects logistic regression with random cluster (hospital) effects allowing inclusion of baseline risk factors such as co-morbid disease and ASA score and adjustment for a fixed time effect between 5-week periods. Patients will be excluded during the five week period immediately after randomisation. Baseline data collected from the first time period will be tabulated by order of implementation, grouping the clusters into three groups of five clusters. This will include 90-day mortality, mean age, sex, admitting specialty, ASA score and five stated process measures (see above). We will examine the adequacy of our randomisation and include any hospital level variable unbalanced at baseline in our final model. The patient level covariates included will be finalised in a statistical analysis plan prior to analysts becoming unblinded to randomisation group. Secondary outcomes will be 180-day mortality, hospital re-admission within 180 days and duration of hospital stay. The latter will be analysed as time to event using a Cox proportional hazard's model with fixed and random effects. Process measures will be analysed in the same way using either logistic or Cox proportional hazards. Total inpatient days will be analysed using a mixed effects regression model after

transforming the data to allow for non-normality if necessary. Between-hospital differences will be described using percentiles. In supplementary analyses, the development of the intervention effect within hospitals over time (learning effect) will be investigated, as will possible intervention by cluster interactions. It is not anticipated that clusters will withdraw from data collection but in this instance, the primary analysis will include only hospitals that have collected data across the whole time period and secondary analysis will use multiple imputation of missing data. No interim analyses are planned.

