#### 3. SUMMARY

Short title	EPOCH Trial
Methods	Multi-centre, stepped wedge cluster randomised trial
Research sites	90 NHS Trusts, grouped into 15 clusters, in the United Kingdom
Objective	To evaluate the effect of a quality improvement intervention to promote the implementation of an integrated peri-operative care pathway on survival at 90 days following emergency laparotomy
Number of patients	27,450 patients
Inclusion Criteria	Patients aged 40 years and over undergoing non-elective open abdominal surgery in participating hospitals will be eligible for inclusion in the data analysis. The following patients will be excluded: simple appendicectomy, gynaecological laparotomy, surgery related to organ transplant, laparotomy for traumatic injury, laparotomy to treat complications of recent elective surgery and patients whose data has previously been included in the trial.
Statistical analysis	The stepped wedge design is a matched design with before and after comparisons for each cluster randomised. 90-day mortality will be modelled using mixed effects logistic regression with random cluster (hospital) effects allowing inclusion of baseline risk factors. Secondary outcomes, 180-day mortality, hospital re-admission within 180 days and duration of hospital stay, will be analysed as time to event using a Cox proportional hazard's model.
Proposed Start Date	March 2014
Proposed End Date	April 2017
Study Duration	30 months

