#### 7.2 Randomisation

An independent statistician will randomise the clusters and keep randomisation records prior to the beginning of the data collection. Simple randomisation will be used to randomise one cluster of hospitals to receive the intervention in each of the fifteen time periods 2 to 16. Local investigators will be notified 12 weeks in advance of the start date for the quality improvement project at their hospital.

[figure not shown]

Figure 2. Cluster randomisation diagram

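### The primary model has random effects for hospital only, although geographic clusters of six hospitals are randomised; if hospitals within a cluster are correlated, its standard error is too small and the type I error exceeds 5%

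*Protocol*

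**What the plan says.** Sections 6.3 and 7.2 make the geographic cluster the unit of randomisation: "Simple randomisation will be used to randomise one cluster of hospitals to receive the intervention", one cluster per step, in periods 2 to 16. There are 15 clusters of six hospitals, and the six hospitals of a cluster cross over together.

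The primary model is fixed at a different level. Section 8.2 says: "In the primary analysis, 90-day mortality will be modelled using mixed effects logistic regression with random cluster (hospital) effects", with a fixed effect for each 5-week period and the transition period excluded. The Summary repeats it: "mixed effects logistic regression with random cluster (hospital) effects". The protocol states no term for the geographic cluster, no cluster-robust standard error and no permutation test.

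Section 8.1 gives 92% power "assuming independent hospital effects". It then warns: "In practice, power may be reduced by correlation between hospitals within clusters and by variation in case-load between hospitals". It continues: "The worst case scenario is one where each of the 15 clusters functions effectively as a single large hospital", for which power is put at 83%. That figure also includes an adjustment for variable case-load.

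**The concern.** The treatment sequence is assigned to 15 units, and the model analyses 90. A random intercept per hospital protects the standard error only if hospitals in the same geographic cluster are no more alike than hospitals in different ones. Section 6.1 forms the clusters around staff rotation and referral patterns, and section 6.4.2 adds regional relationships, so some similarity within clusters is plausible. Section 8.1 allows for it when it states power. Section 8.2 does not carry it into the analysis, so the lower power bound rests on 15 effective units while the model written down has 90.

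At stake is the primary test. If the correlation is positive, the confidence interval for the effect on 90-day mortality is too narrow and the false-positive rate is above the nominal 5%.

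**Working it through.** **Inputs from the protocol.** 15 clusters × 6 hospitals and 17 periods (6.3). 18 patients per hospital per period, baseline mortality 25%, effect 3 points, between-hospital coefficient of variation 0.15, two-sided 5% (8.1). One transition period per hospital dropped (8.1, 8.2), leaving 90 × 16 = 1,440 hospital-periods.

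**Assumed, because the protocol gives no value.** ρ, the share of between-hospital variance that is common to the hospitals of one cluster. The range 0 to 1 is shown.

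**Step 1: reproduce the stated power.**
- Between-hospital SD = 0.15 × 0.25 = 0.0375, so τ² = 0.00141.
- Sampling variance of a hospital-period = 0.25 × 0.75 / 18 = 0.0104.
- D holds the period effects and the intervention indicator. V_m is the covariance under independent hospital intercepts. The standard error (SE) is the square root of the intervention element of (D′V_m⁻¹D)⁻¹ = 0.00885, or 0.885 points.
- Power = Φ(0.03/0.00885 − 1.96) = Φ(1.43) = 92.3%. The protocol states 92%, so the figure reproduces.

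**Step 2: does the before-after structure remove a constant cluster effect?** Only partly. Each hospital contributes 16 × 18 = 288 analysed patients, so its mean has sampling variance 0.1875/288 = 0.00065, against τ² = 0.00141. A random intercept therefore still uses comparisons between hospitals, and it weights them as if there were 90 independent units.

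**Step 3: true standard error of the written model.** Let V have hospital variance (1 − ρ)τ² and cluster variance ρτ². The estimator's weights are L = (D′V_m⁻¹D)⁻¹D′V_m⁻¹, and its true variance is the intervention element of L V L′. The model-based SE stays at 0.885 points because total variance per hospital is unchanged. Then

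type I error = 2Φ(−1.96 × 0.885 / true SE).

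Example, ρ = 0.5: true SE 1.036, ratio 0.885/1.036 = 0.854, 2Φ(−1.67) = 9.4%.

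| Share ρ at cluster level | True SE (points) | Type I error, hospital-only model | Power with both intercepts, constant case-load |
|---|---|---|---|
| 0 | 0.885 | 5.0% | 92.3% |
| 5% | 0.90 | 5.4% | 91.5% |
| 10% | 0.92 | 5.9% | 90.9% |
| 25% | 0.96 | 7.2% | 89.5% |
| 50% | 1.04 | 9.4% | 88.3% |
| 75% | 1.10 | 11.6% | 87.6% |
| 100% | 1.17 | 13.7% | 87.1% |

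**Step 4: simulation with binary outcomes.** Logistic mixed models were fitted by penalised quasi-likelihood with estimated variances, under no intervention effect. Between-hospital SD was 0.0375/(0.25 × 0.75) = 0.20 on the logit scale, with 500 runs per setting.

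| ρ | Hospital intercept only | Cluster and hospital intercepts |
|---|---|---|
| 0 | 4.8% | 5.0% |
| 25% | 6.0% | 3.8% |
| 50% | 9.2% | 4.8% |
| 100% | 18.0% | 6.0% |

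Monte Carlo error is about 1 point near 5% and √(0.18 × 0.82/500) = 1.7 points at 18%. The simulation agrees with the table in step 3 up to ρ = 50% and is higher at 100%.

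**Step 5: cluster-by-period variation.** The protocol gives no figure. With an assumed SD of 2 points and ρ = 50%, the hospital-only model has a type I error of 11.7%, and power under a model that includes this term is 81.7%. With smaller amounts (2% to 20% of between-hospital variance), the model with both intercepts gives 5.2% to 6.4%.

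**The case against.** The strongest reply is that the excess is conditional. The protocol gives no within-cluster correlation and says only that power may be reduced. At ρ = 0 the written model holds 5%, and at a 5% or 10% share the error is 5.4% or 5.9%. This stands. A reader might infer that the 5% level is certainly lost, or that 14% or 18% is the expected error rate. The document supports neither. Those figures belong to what section 8.1 calls its worst case.

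A reader might also infer that the power statement is wrong. It is not shown to be. The 92% reproduces and carries its condition in the same sentence. For 15 units at constant case-load the calculation gives 87.1% rather than 83%, but the stated figure includes a case-load adjustment whose inputs are not given, so it cannot be called an error.

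Other replies carry less weight. The wording in brackets could be called loose, but it equates cluster with hospital and appears twice. An unseen analysis plan might add a cluster term, but section 8.2 leaves only the patient-level covariates to that plan and states the random effect itself. The supplementary look at intervention-by-cluster interactions does not change the primary standard error. Case-mix adjustment does not remove the problem either: with between-hospital variance halved, the error at a 50% share is still 9.6%.

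**Conclusion.** The concern holds in conditional form. The mismatch between the randomised unit (15 geographic clusters) and the random effect (90 hospitals) is explicit. If hospitals within a cluster are positively correlated, as section 8.1 foresees, the primary standard error is too small and the test exceeds its nominal level. The analytic range is 5.0% at no shared variance to 13.7% when all of it is shared, with about 18% in simulation at that extreme.

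Confidence is high in the mismatch and in the direction of the error. The size is uncertain because it depends on an unstated correlation. The figures assume the plan's mortality, coefficient of variation and constant case-load, and a cluster effect constant over time except in step 5. It should be corrected before the analysis, because it concerns the primary test and the remedy is cheap.

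**What to change.** In section 8.2 and the Summary, specify random intercepts for the randomised geographic cluster and for hospital within cluster. Because only 15 clusters are randomised, add as a check either a small-sample correction or a permutation test over the randomised cluster order. Treat a random cluster-by-period term as a sensitivity analysis, since the protocol gives no basis for its size. State what is done if a variance component is estimated as zero. The 92% statement in section 8.1 needs no change.

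The cost is wording and slightly wider intervals. Power at constant case-load falls from about 92% at zero correlation to 89.5% at a 25% share and 87–88% at 50–100%. It would be lower if there is also cluster-by-period variation: about 82% under the assumed 2-point SD at a 50% share.

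### Hospital-level covariates enter the primary model through an undefined chance-imbalance trigger, judged with the randomised order in view, and period-1 mortality is not barred

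*Protocol*

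**What the plan says.** Protocol section 8.2 specifies a mixed-effects logistic model for 90-day mortality with random hospital effects, fixed effects for the 5-week periods, and baseline risk factors. On covariates it says four things.

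- How balance is displayed: "Baseline data collected from the first time period will be tabulated by order of implementation, grouping the clusters into three groups of five clusters".
- What the table holds: "This will include 90-day mortality, mean age, sex, admitting specialty, ASA score and five stated process measures (see above"). That is ten items, with the primary outcome first.
- What follows from it: "We will examine the adequacy of our randomisation and include any hospital level variable unbalanced at baseline in our final model".
- The safeguard: "The patient level covariates included will be finalised in a statistical analysis plan prior to analysts becoming unblinded to randomisation group".

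On who is analysed, the same section says "all patients recorded in the data base during the 85-week period will be included", with one exception: "Patients will be excluded during the five week period immediately after randomisation". Section 6.3 places the starts in periods 2 to 16, so that exception never removes period 1. Section 7.2 says the order of clusters is drawn by simple randomisation.

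**The concern.** This is a positive rule for the primary model, not a detail left to the SAP. An SAP that followed the protocol would inherit it. It has three weaknesses.

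1. **It selects on chance.** With a randomised order, an imbalance across that order says nothing about whether a variable predicts death. A strong predictor that happens to be balanced stays out, and a weak one that happens to be unbalanced goes in.
2. **It leaves a choice open after allocation is visible.** The table is laid out by implementation order, which is the allocation. No variables are listed, and no test, threshold or size of difference defines imbalance. The pre-unblinding safeguard does not extend to hospital-level variables.
3. **It does not exclude the outcome.** A hospital's period-1 death rate is a hospital-level quantity in the baseline table. If judged unbalanced, it could enter as a predictor while the same deaths are counted in the response.

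At stake is whether the primary model is fixed in advance, in a trial that aims to be definitive.

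**Working it through.** **Inputs.** From section 8.1: mortality 25%, target 22%, between-hospital coefficient of variation 0.15, 18 patients per hospital per 5 weeks, start period dropped, two-sided 5%. From section 6.3: 15 clusters of 6 hospitals, 17 periods, starts in periods 2 to 16. Hence:

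- hospital SD = 0.15 × 0.25 = 0.0375, so hospital variance τ² = 0.001406;
- variance of one hospital-period rate given the hospital, s² = 0.25 × 0.75 / 18 = 0.010417.

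**The plan's own figure.** Use the weighted least squares variance of Hussey and Hughes. Each hospital contributes 16 periods with covariance τ²J + s²I, and there are 17 fixed period effects and one intervention effect. The SE of the effect is 0.00885. Power = Φ(0.03/0.00885 − 1.96) = 92.3%, which reproduces the stated 92% for independent hospitals.

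**How much imbalance chance produces.** Each third of the order has 5 × 6 × 18 = 540 period-1 patients. The SE of a group's mortality is:

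- independent hospitals: √(0.1875/540 + 0.001406/30) = 2.0 points;
- each cluster acting as one hospital: √(0.1875/540 + 0.001406/5) = 2.5 points.

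The SE of a difference between two groups is √2 times these, 2.8 and 3.5 points. By the distribution of the range of three normal means, the highest and lowest groups differ by 5 points or more in about 18% and 34% of properly randomised trials respectively. Visible imbalance in mortality is thus quite possible when nothing is wrong.

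**What period-1 mortality does on both sides of the model.** If period 1 is removed from the response, the coefficient on a hospital's period-1 rate should equal the reliability of that rate:

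τ²/(τ² + s²) = 0.001406/0.011823 = 0.119.

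If period 1 stays in, it is one of 16 analysed periods, and for it the covariate predicts itself with slope 1:

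(15 × 0.119 + 1)/16 = 0.174.

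The apparent residual hospital variance falls from 0.001406 × (1 − 0.119) = 0.00124 to (15/16)² × (0.00124 + 0.010417/15) − 0.010417/16 = 0.00105. So the model credits the covariate with more than it explains and understates hospital variation.

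**What that does to inference.** A simulation of 4,000 trials with no intervention effect used the same design and a linear mixed model on hospital-period rates. Imbalance in mortality was flagged by a three-group analysis of variance at p < 0.05, an assumed criterion because the protocol gives none.

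| Handling of period-1 mortality | Coefficient | Hospital variance | Type I error |
|---|---|---|---|
| Not a covariate | – | 0.00140 | 5.4% |
| Always a covariate, period 1 kept in outcome | 0.175 | 0.00105 | 6.1% |
| Always a covariate, period 1 dropped from outcome | 0.119 | 0.00124 | 5.2% |
| Covariate only if flagged, period 1 kept | – | – | 5.5% |

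The simulated coefficients and variances agree with the algebra. The Monte Carlo standard error of each error rate is about √(0.055 × 0.945/4000) = 0.4 points. With the covariate always in and period 1 kept, the mean model SE (0.00865) is below the actual SD of the estimate (0.00902). The mean estimate is 0.0002 with or without the covariate, so no bias is added. Mortality was flagged in 5.2% of trials. In those, adjustment moved the estimate by 0.28 points on average and 0.76 at most, against a target of 25 − 22 = 3 points. Relative to the SE of 0.885 points, these shifts are about 0.3 and 0.85 SE.

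**The case against.** The strongest reply is that the rule hardly matters. The random hospital effect already absorbs most stable hospital differences, so adding such a variable changes little, and the simulated type I error under flag-then-adjust is indistinguishable from that without it. With only 15 units ordered by simple randomisation, adjusting for a chance imbalance in a prognostic hospital variable is also a reasonable aim. Period-1 patients all have surgery before any hospital is activated, so their table shows no before-and-after contrast. An SAP not seen here might mask the groups or set a criterion.

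Much of this stands, and it rules out some stronger readings.

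- A reader might infer that section 8.2 contradicts itself by promising a fixed model before unblinding. It does not. "finalised in a statistical analysis plan prior to analysts becoming unblinded to randomisation group" refers to patient-level covariates, and the imbalance rule refers to hospital-level ones. The weakness is that the safeguard is too narrow.
- A reader might take all ten tabulated items as candidates, each tested at 5%, and conclude that 1 − 0.95¹⁰ = 40% of sound trials would gain a spurious covariate. The protocol states no threshold and does not call the table the candidate list. Several items are patient-level, and independence is implausible. The same sum gives 10% at a 1% threshold and 65% at a 10% threshold, so it describes the assumption, not the plan.
- A reader might say the p-value and interval lose their nominal meaning. Under mechanical use, 5.5% against 5.4% does not support that.
- The protocol does not say that period-1 mortality will be a covariate, only that it is tabulated. The point is that nothing excludes it.

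The reply does not remove the discretion. The simulation bounds one variable under one fixed rule. It does not bound a choice among unlisted variables with no criterion, made with the allocation in view. Prognostic imbalance is better handled by naming prognostic variables beforehand.

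**Conclusion.** The concern holds as a fault of pre-specification. The hospital-level part of the primary model depends on an undefined judgement of chance imbalance, made from a table laid out by allocation and outside the blinding safeguard. Period-1 mortality could become both predictor and outcome.

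The numerical harm under a mechanical rule is small: type I error of about 5.5%, or 6.1% in the extreme case, against 5.4%, no mean bias, and a typical shift of about 0.3 points when mortality is flagged. A shift near the 0.8-point maximum could change a conclusion close to the significance boundary, but it would be rare.

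These figures assume a linear approximation to the logistic model, equal case-load, independent hospitals and a 5% flagging test. They do not measure the effect of free choice by an analyst, which is the real issue. The change is worth making because it is easy and protects the primary analysis, not because the trial would otherwise be invalid.

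**What to change.** In section 8.2, delete the sentence that admits hospital-level variables on the strength of observed imbalance. In its place:

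- state that all covariates, hospital-level and patient-level, will be named in the SAP before analysts are unblinded, chosen on prognostic grounds and kept whatever the baseline table shows (or state that no hospital-level covariates will be used);
- state that period-1 mortality will not be a covariate while period 1 is part of the outcome;
- keep the table by order of implementation as description only.

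The cost is one sentence removed and two or three added. No data are lost. The 92% power figure comes from a model without such covariates, so it is unchanged.

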#### 6.3 Study design

Multi-centre, stepped wedge cluster randomised trial conducted in at least 90 NHS hospitals over an 85 week period, divided into 17 time period of 5 weeks. Hospitals will be grouped into fifteen clusters of six on a geographical basis. The quality improvement intervention will commence in one cluster each five week step from the 2nd to the 16th time period, with the order of clusters determined by computer based randomisation. The stepped wedge design allows delivery of the intervention at an organisational level with evaluation of outcome measures at a patient level. Structuring the quality improvement intervention through a staged activation of sites in a random order provides important methodological advantages. The design allows us to control adoption bias and adjust for time-based changes in the background level of patient care in the statistical analysis. A key strength of the stepped wedge design is that we can offer the quality improvement project to every site which takes part.

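### If hospitals withdraw from data collection, the primary analysis drops all their recorded patients, which conflicts with the intention-to-treat set and selects hospitals on post-randomisation behaviour

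*Protocol*

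**What the plan says.** All the relevant text is in Protocol section 8.2.

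- **Analysis set.** The analysis is intention-to-treat, meaning that "all patients recorded in the data base during the 85-week period will be included", with exposure assigned by randomisation. To protect this, "The intervention start date for each cluster will be fixed regardless of whether implementation proceeds on time".
- **Planned exclusion.** "Patients will be excluded during the five week period immediately after randomisation". This removes one period from every hospital by design.
- **Model.** "90-day mortality will be modelled using mixed effects logistic regression with random cluster (hospital) effects", with a fixed effect for each 5-week period.
- **Contingency.** Withdrawal is treated as unlikely. Should it happen, the main result is restricted: "the primary analysis will include only hospitals that have collected data across the whole time period". Incomplete hospitals are then left to a supporting analysis, for which the plan is brief: "secondary analysis will use multiple imputation of missing data".

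The trigger is worded for clusters and the restriction for hospitals. Section 6.3 makes these different units: "Hospitals will be grouped into fifteen clusters of six on a geographical basis". The protocol does not say what counts as having collected data for the whole period. For the primary model, section 8.2 defers only the patient-level covariates to the statistical analysis plan, so the contingency rule is fixed here.

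**The concern.** Take a hospital that records patients from period 1 and stops in period 12. The intention-to-treat sentence includes its patients from periods 1 to 11; the contingency sentence excludes them. Both cannot govern the primary analysis.

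Whether a hospital is complete becomes known only after randomisation. Start dates are fixed whatever happens to implementation, which stops uptake from influencing the comparison. The contingency rule lets hospital behaviour back in by another route. If hospitals that stop recording respond to the intervention differently from those that continue, the remaining hospitals no longer estimate the effect across all randomised hospitals. At stake are the population behind the primary result and the use of sound data that the model could handle.

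**Working it through.** **1. Reproduce the stated power.** Inputs from sections 6.3 and 8.1: 90 hospitals in 15 clusters of 6; 17 periods; one cluster starting in each of periods 2 to 16; 18 patients per hospital per period; mortality 25% falling to 22%; between-hospital coefficient of variation 0.15; independent hospitals; commencement period removed; two-sided 5% level.

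- Expected patients: 90 × 17 × 18 = 27,540, as section 8.1 states. Transition patients: 90 × 18 = 1,620. Analysable: 25,920.
- Between-hospital SD: τ = 0.15 × 0.25 = 0.0375. Variance of a hospital-period mean: 0.25 × 0.75 / 18 = 0.01042.
- Hussey and Hughes variance: for each hospital k, V_k = 0.01042·I + τ²·J (I the identity matrix, J all ones). D_k holds the period indicators and the exposure indicator for its retained periods. The variance of the effect is the exposure element of (Σ D_k′ V_k⁻¹ D_k)⁻¹.
- The standard error is 0.00885. Power = Φ(0.03/0.00885 − 1.96) = Φ(1.43) = 92.3%, matching the stated 92%.

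**2. Show that the model does not need complete hospitals.** The calculation above already omits one period from every hospital. Further missing periods only shorten D_k. The planned mixed logistic model likewise uses whichever hospital-periods have data.

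**3. Count what the rule discards.** A full hospital has 17 × 18 = 306 expected patients, of whom 16 × 18 = 288 are analysable. A hospital that stops has fewer, because patients after stopping were never recorded. Assume stopping in a random period from 3 to 17, so that 2 to 16 periods are recorded, 9 on average:

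- Recorded: 9 × 18 = 162.
- The transition period falls within the recorded part with probability 16/30 = 8/15, removing 18 × 8/15 = 9.6.
- Analysable but discarded: 162 − 9.6 = 152.4 per hospital, or 1,372 for 9 hospitals and 2,743 for 18. A simulation of the 9-hospital case averaged 1,388.

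**4. Isolate the power cost of the rule.** The right comparison is dropping the hospital against keeping what it recorded, not against having no withdrawal. The number of hospitals is assumed. Values are averages over random choices of hospital and stopping period, and vary by about 0.1 point between runs.

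| Hospitals stopping | Drop hospital (SE) | Keep recorded data (SE) | Cost of rule |
|---|---|---|---|
| 1 | 92.1% (0.00890) | 92.2% (0.00888) | 0.1 point |
| 9 | 89.5% (0.00934) | 91.1% (0.00907) | 1.6 points |
| 18 | 85.7% (0.00991) | 89.7% (0.00931) | 4.0 points |

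If hospitals miss only one period and are kept, power stays between 92.1% and 92.3% for 1 to 18 hospitals.

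**5. Illustrate possible bias.** None of these inputs is in the protocol. Set the true mean effect to zero and let hospital responses vary with an SD of 2 or 3 percentage points. Dropping 9 hospitals at random gave estimates of 0.02 and −0.11 points (simulation error 0.05 to 0.06), so close to zero. Dropping the 9 worst responders gave −0.36 and −0.52 points; dropping the 18 worst gave −0.77 and −1.02. The target effect is 3 points. This is an extreme case: stopping is perfectly aligned with poor response, and the benchmark is full data from every hospital. If the better responders stopped, the sign would reverse.

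**The case against.** The strongest defence is that the rule is dormant. It applies only on withdrawal, which the protocol does not expect, and it is stated in advance and paired with a secondary analysis by multiple imputation. The intention-to-treat sentence already has an exception for the transition period. Data come through a national audit that also runs in hospitals outside the intervention (section 7.4), so ending audit entry and disengaging from quality improvement are different acts.

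Much of this stands. It lowers the priority and rules out several stronger readings that a reader might infer:

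- **That the effect is biased upward.** Section 6.4.2 feeds process data back to frontline teams, so a link between recording and engagement is plausible. Nothing in the protocol shows that hospitals which stop are those that benefit least.
- **That a single five-week gap costs a hospital all 306 patients.** The trigger is withdrawal, and completeness is undefined. Even on the literal reading, a missed period outside the transition leaves 15 × 18 = 270 analysable patients to discard. This is an ambiguity to remove, not a stated rule.
- **That multiple imputation cannot work.** Patients never entered have no records to complete, but the protocol does not fix the level of imputation, and that detail may properly sit in the analysis plan.
- **That already planned linkage could fill unrecorded periods.** Section 7.3 links patients recorded in the audit, and section 6.1 limits the core dataset to audit data.

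Two parts of the defence fail. The transition exclusion is set by the randomised schedule for every hospital, whereas completeness depends on the hospital's own conduct. And stating a selection rule in advance does not make the selection neutral.

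**Conclusion.** The point holds as a defect in a contingency rule. If withdrawal occurs, section 8.2 gives two incompatible primary analysis sets, and the restrictive one selects hospitals on post-randomisation behaviour while discarding data that the model can use.

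The main issue is the analysis set, with a possible bias whose direction and size the protocol cannot settle. Power is secondary: the rule costs about 0.1 point for one hospital and 1.6 points for nine, assuming the section 8.1 inputs and random stopping between periods 3 and 17. The protocol gives no basis for expecting 9 or 18 withdrawals; these numbers only show the scale. Keeping recorded data does not remove all bias from informative stopping, since a stopped hospital contributes less post-intervention data, but it avoids adding the selection made by the rule.

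This should be fixed. It does not undermine the design, because the rule has no effect unless withdrawal happens.

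**What to change.** Amend the contingency text in section 8.2, before the analysts are unblinded:

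1. State that the primary analysis uses all recorded eligible patients from every randomised hospital, classified by randomised start date, whether or not the hospital contributed to every period. Keep the planned transition-period exclusion.
2. Make the analysis restricted to complete hospitals a sensitivity analysis.
3. Define what collecting data for the whole period means, so that a short gap is distinguished from withdrawal, and use one unit, hospital or cluster, for both trigger and restriction.

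Multiple imputation can remain a secondary analysis, with its level set out in the statistical analysis plan. The cost is a change of wording in the protocol and analysis plan, with no new patients or data.
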